### **7.9 Duration of Therapy and Criteria for Removal from Study**

In the absence of treatment delays due to adverse event(s), treatment may continue until one of the following criteria applies:

- Disease progression,
- Intercurrent illness that prevents further administration of treatment,
- Unacceptable adverse event(s),
- Subject decides to withdraw from the study, or
- General or specific changes in the subject's condition render the subject unacceptable for further treatment in the judgment of the investigator.

Patients may discontinue study treatment for any reason. Patients who elect to discontinue study treatment should be encouraged to continue in the study so that follow-up information on disease progression and survival status may be obtained. However, patients may elect to withdraw consent and decline further participation in the trial. All patients will be followed until disease progression, withdrawal of consent, death or loss to follow up.

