2. Includes baseline symptoms as well as a detailed history of prior cancer therapies, especially MM therapies, including start and stop dates, disease progression during or after therapy, as well as discontinuations due to intolerance or any other serious illness. Collect data on cigarette smoking status and, if current smoker, counsel regarding smoking cessation per institutional guidelines.
3. Dose intensity assessments involve the use of subject medication diaries, provided on C1D1 and assessed on day 1 of every cycle beginning at cycle 2.
4. QOL assessment as measured by the Functional Assessment of Cancer Therapy - MM (FACT-MM). See Appendix 6.
5. Telephone call (or visit) for:
  - a. Follow-up assessment to evaluate adverse events.
  - b. Durability of Response and Survival Follow-up: After treatment discontinuation, if possible and feasible for patients whose disease is not progressing, a telephone call will be made to the patient (or the patient's family) every 3 months for 18 months to inquire about the patient's survival, MM status, and information on any antineoplastic therapies utilized since discontinuation of study treatment, as well as available SPEP with serum immunofixation, UPEP with urine immunofixation, serum FLC, quantitative Ig levels, and plasmacytoma assessment when clinically appropriate.
6. Complete serum chemistry must include serum potassium and magnesium levels.
7. For women of childbearing potential, a serum hCG pregnancy test must be performed during Screening and at EoT Visit. After an initial negative serum hCG pregnancy test during Screening, urine pregnancy tests may be performed instead of serum testing. Women of childbearing potential require two negative pregnancy tests prior to receiving the first dose of study treatment (at Screening and at C1D1).
8. Response criteria include SPEP, serum immunofixation, quantitative Ig levels, and serum FLC assay on C1D1 and measurements must be taken either on Day -1 or pre-dose on C1D1. These are in addition to the disease assessments performed during Screening for enrollment. UPEP (24-hr urine) and urine immunofixation may be omitted on C1D1 if performed adequately during screening within  $\leq$  7 days.

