### **7.10 Duration of Follow Up**

Subjects will be followed for 12 months after end of treatment (EoT) visit or until death, whichever occurs first. Subjects removed from study for unacceptable adverse events will be followed until resolution or stabilization of the adverse event.

End of study will occur after the last patient to be enrolled has completed the one year follow up period, died, withdrawn consent, or been lost to follow up, whichever comes first.

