### **7.10.2 Duration of Response and Survival Follow Up**

Every three months ( $\pm$  14 days) for 12 months after the EoT visit, if feasible and clinically appropriate, the following assessments should be obtained for patients who have not progressed to assess durability of response:

- SPEP and serum protein immunofixation
- UPEP (24-hour urine) and urine protein immunofixation
- Serum FLC
- Quantitative Ig levels
- Bone marrow aspirate, as clinically indicated, to assess progression
- Re-assessment of plasmacytomas by physical examination (if detected by physical examination at Screening)
- Skeletal survey (imaging) for bone lesions, including tumor measurements as clinically indicated to document response, at frequency determined by the Investigator

If these procedures cannot be obtained, at a minimum, a telephone call will be made to the patient (or the patient's family) every 3 months to inquire about the patient's MM status, general health, and information on any antineoplastic therapies utilized since discontinuation of study treatment.

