### **8.2 Participant Discontinuation/Withdrawal from the Study**

Participants are free to withdraw from participation in the study at any time upon request. Patients who elect to discontinue study treatment should be encouraged to continue in

the study so that follow-up information on disease progression and survival status may be obtained. However, patients may elect to withdraw consent and decline further participation in the trial. All patients will be followed until disease progression, withdrawal of consent, death or loss to follow up.

An investigator may discontinue or withdraw a participant from the study for the following reasons:

- Pregnancy
- Significant study intervention non-compliance
- If any clinical adverse event (AE), laboratory abnormality, or other medical condition or situation occurs such that continued participation in the study would not be in the best interest of the participant
- Disease progression
- If the participant meets an exclusion criterion (either newly developed or not previously recognized) that precludes further study participation
- Participant lost to follow-up after three attempts to contact subject to schedule study visit.

The reason for participant discontinuation or withdrawal from the study will be recorded on the eCRF. Subjects who sign the informed consent form but do not receive the study intervention may be replaced. Subjects who sign the informed consent form, and receive the study intervention, and subsequently withdraw, or are withdrawn or discontinued from the study, will not be replaced.

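### The follow-up passages disagree on whether patients are followed for survival after progression, and section 12.4.3 lacks usable censoring dates for OS, PFS and DOR

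*Combined protocol and SAP*

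**What the plan says.** **Passages that stop at progression.** Sections 7.9 and 8.2 both say "All patients will be followed until disease progression, withdrawal of consent, death or loss to follow up". In each, the sentence comes shortly after one encouraging patients who stop treatment to stay in the study "so that follow-up information on disease progression and survival status may be obtained". Section 8.2 adds a list introduced by "An investigator may discontinue or withdraw a participant from the study for the following reasons", and disease progression is on it. Footnote 5b to Table 2, which describes the survival call, says that where feasible, "for patients whose disease is not progressing, a telephone call will be made to the patient" or family, "every 3 months for 18 months to inquire about" survival, myeloma status and later therapy.

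**Passages that do not stop at progression.** Section 7.10 says "Subjects will be followed for 12 months after end of treatment (EoT) visit or until death, whichever occurs first". Section 8.1 says that stopping treatment is not leaving the study. Table 2 and section 6.1.3.2 plan quarterly response and survival contacts for 12 months after the last dose and set no progression limit.

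**A mixed passage.** Section 7.10.2 says "the following assessments should be obtained for patients who have not progressed to assess durability of response". Its fallback telephone call asks about myeloma status, "general health, and information on any antineoplastic therapies utilized since discontinuation of study treatment". It names neither survival nor date of death.

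**Analysis.** Section 12.4.3 measures OS from start of therapy to death from any cause and analyses it as PFS is analysed. PFS is censored, for patients who drop out before study end, at the last assessment showing no evidence of disease. DOR uses the same anchor for patients who have not progressed.

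**The concern.** OS needs deaths after progression, which in relapsed myeloma is where most deaths would be expected. If observation ends at progression, patients leave the risk set just as their hazard of death rises. That censoring is informative, and Kaplan-Meier then overstates survival. Safety reporting would not recover these deaths, because section 13.2 excludes fatal progression from SAE reporting. Post-progression deaths that are not collected during the trial may be hard to recover later.

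The censoring wording is a second, separate gap. Entry requires measurable disease (section 4.2). Under Appendix 4, patients in partial response, minimal response or stable disease still have evidence of disease. Read literally, an event-free patient in one of those states has no valid censoring date for PFS or, if a responder, for DOR. A patient who is event-free at study end without dropping out has no stated PFS rule at all. OS inherits these rules and has no last-known-alive date of its own.

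**Working it through.** **1. The passages side by side**

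| Place | Who is followed | How long |
|---|---|---|
| 7.9, 8.2 | all patients | until progression, withdrawal of consent, death or loss |
| Footnote 5b | not progressing | 18 months |
| 7.10.2 assessments | not progressed | 12 months after EoT visit |
| 7.10 | all subjects | 12 months after EoT visit, or death |
| Table 2, 6.1.3.2 | no progression limit | 12 months after last dose |
| 7.10.1, 30-day contact | no progression limit | once |

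No sentence says which passage governs. The documents give no design figure for OS, PFS or DOR, so there is none to reproduce.

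**2. Illustration of size**

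Inputs from section 2.2.2 (the cited clarithromycin-pomalidomide-dexamethasone study): median PFS 7.7 months, median OS 19.2 months. Assumptions that are not in the documents: constant hazards, end of treatment at progression, and a share f of PFS events that are deaths, taken as 5% to 30%.

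- PFS hazard: L = ln 2 / 7.7 = 0.0900 per month.
- True survival: S(t) = exp(-Lt) + (1-f) L [exp(-Lt) - exp(-mt)] / (m - L), where m is the death hazard after progression, solved so that S(19.2) = 0.50.
- If observation ends w months after progression, the Kaplan-Meier curve tends to the one with hazard [f L P0 + m P1w] / [P0 + P1w]. P0 = exp(-Lt), and P1w is the probability of being alive having progressed within the last w months.

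| f | m | w = 30 days (stop at progression, 30-day contact credited) | w = 12 months (7.10 for everyone) | w = 18 months |
|---|---|---|---|---|
| 5% | 0.0797 | 82% | 52% | 50% |
| 10% | 0.0743 | 77% | 52% | 50% |
| 20% | 0.0628 | 67% | 51% | 50% |
| 30% | 0.0502 | 58% | 51% | 50% |

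Each entry is estimated survival at 19.2 months; the true value is 50%.

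In deaths, 26 x 0.5 = 13 are expected by 19.2 months. With stop-at-progression and the 30-day contact, about 2.6 (f = 5%) to 7.1 (f = 30%) of the 13 are collected, so about 6 to 10 are missed. Under 7.10 about 1 is missed.

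**3. Comparison with chance**

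For 26 fully followed patients the 95% sampling range at a true 50% is 0.50 ± 1.96 x sqrt(0.25/26) = 0.50 ± 0.19, or 31-69%. The biased readings at f = 20% and 30% (67% and 58%) fall inside it; those at 5% and 10% (82% and 77%) fall above it.

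**4. A second benchmark**

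The cited selinexor-dexamethasone study (section 2.2.1; PFS 3.7, OS 8.6 months) gives 64-71% at 8.6 months with the 30-day contact and f of 10-20%. The direction is the same.

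**The case against.** The strongest reply is that the protocol, read as a whole, already follows everyone for 12 months. Section 7.10 is the section on follow-up duration. Its end-of-study sentence lists completed one-year follow-up, death, withdrawn consent and loss, but not progression. Section 8.1 separates stopping treatment from leaving the study, the schedule has a survival column, and the 8.2 list only permits withdrawal. A quarterly call to patient or family would usually bring a death to light, and section 12.4.2 plans a listing of deaths. On that reading the bias is 1 to 2 percentage points, negligible with 26 patients.

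Most of this stands as evidence of intent, but it does not settle the instruction. Section 8.1 sends staff to the remaining procedures, and the text describing the survival call, footnote 5b, leaves out progressed patients. The 7.10.2 fallback replaces assessments that are themselves limited to patients who have not progressed, and it asks for no date of death. A listing of deaths is an output and does not collect them.

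Three stronger readings are tempting and are not supported:
- That OS deaths will certainly be lost. The text is contradictory, so loss is a risk that depends on which passage a site follows.
- That nothing is known after progression, which would put the reading at 60-92% on the same inputs. The 30-day contact has no progression limit and must be credited.
- That the distortion exceeds chance. With the 30-day contact credited, part of the range lies within sampling error.

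On censoring, the authors probably meant no evidence of progression. Read that way, there is no DOR or PFS bias from the anchor, and none is claimed here. Death already counts as a DOR event in sections 10.2 and 12.4.3, so that needs no change.

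**Conclusion.** The contradiction is in the text and should be resolved. Twelve months for all patients is probably the intention. A site working from 7.9, 8.2 or footnote 5b would nevertheless miss most post-progression deaths and bias OS upward, to roughly 58-82% against 50% in the illustration. That range rests on medians from a different regimen in more heavily pretreated patients (median 5 prior therapies, against two to four lines here), on constant hazards, on end of treatment at progression, and on an assumed share of deaths among PFS events that drives the result. It shows what could happen and is not a forecast. The direction is upward in every case examined.

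The missing last-known-alive date for OS and the missing PFS rule for patients event-free at study end are real omissions. The no-evidence-of-disease anchor is most likely a slip of wording, but as written it leaves the censoring dates to whoever programs the analysis.

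OS, PFS and DOR are exploratory and descriptive. The two-stage response-rate rule does not use them, so this is a change that should be made and not one on which the trial's conclusion depends.

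**What to change.** - Reconcile 7.9, 8.2, 7.10, 7.10.2 and footnote 5b to one survival follow-up period for all treated patients regardless of progression. Settle 12 against 18 months, and whether the clock starts at the last dose or at the EoT visit.
- Have the telephone contact already in the schedule record vital status and, where applicable, date of death.
- In 12.4.3, censor OS at the date last known alive. Censor PFS and DOR, for every patient without an event, at the last adequate assessment without IMWG progressive disease.
- If 12 months is kept, note when reporting OS that the cap may leave a small upward bias.

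The cost is a wording amendment plus quarterly calls to progressed patients: at most 4 per patient at 12 months (4 x 26 = 104), or 6 per patient (156) at 18 months. Sample size, boundaries, alpha and power do not change.

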### **7.10 Duration of Follow Up**

Subjects will be followed for 12 months after end of treatment (EoT) visit or until death, whichever occurs first. Subjects removed from study for unacceptable adverse events will be followed until resolution or stabilization of the adverse event.

End of study will occur after the last patient to be enrolled has completed the one year follow up period, died, withdrawn consent, or been lost to follow up, whichever comes first.

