**Participant Duration:** Participants are estimated to receive study treatment for approximately 10 months, undergo a follow-up assessment 1 month later, and four duration-of-response/survival follow-up assessments every 3 months, for approximately 24 months on study.

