#### **6.1.3.2 Duration of Response and Survival (every 3 months ± 14 days after last dose for 12 months)**

- Telephone contact
- SPEP and serum immunofixation
- UPEP (24-hr urine) and urine immunofixation
- Quantitative Ig levels
- Serum FLC
- Skeletal survey\*
- Plasmacytoma assessment\*
- Bone marrow biopsy and aspirate\*

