### 12.4.3 Analysis of Exploratory Endpoints

Duration of Response (DOR) will be analyzed by Kaplan-Meier descriptive statistics for patients who have a response of sCR, CR, VGPR or PR, as assessed by IMWG criteria. DOR will be calculated as the number of days from the date of the first evidence of response until progression or death. Patients who have not progressed at the time of analysis will be censored at the last available assessment date at which no evidence of disease was observed. Estimates will include the 25th, 50th (median), and 75th percentiles and associated 95% CIs, as well as the number and percentage of censored patients.

The clinical benefit rate (CBR) will be performed by calculating the point estimate of the percentage of patients who have a response of sCR, CR, VGPR, PR or MR, as assessed by IMWG criteria. Analysis will be performed by calculation of the point estimate of CBR, as well as a two-sided 95% CI, using exact methods.

The disease control rate (DCR) will be performed by calculating the point estimate of the percentage of patients who have a response of sCR, CR, VGPR, PR, MR or SD, as assessed by IMWG criteria. Analysis will be performed by calculation of the point estimate of DCR, as well as a two-sided 95% CI, using exact methods.

Progression-free Survival (PFS) will be calculated from the date of start of study therapy to the date of progression based on IMWG criteria, or date of death due to any cause should progression not have occurred. Patients who drop out prior to study end will be censored at the last available assessment date at which no evidence of disease was observed. The analysis of PFS will be based on the Kaplan-Meier method for estimation of summary statistics, and include the 25th, 50th (median), and 75th percentiles and associated 95% CIs.

Overall Survival (OS) will be calculated from the date of start of study therapy to the date of death due to any cause. This analysis will be performed in the same manner as the analysis of PFS.

Patients will be provided medication diaries at the beginning of each cycle. Delivered dose intensity will be assessed on day 1 of each cycle starting on cycle 2; defined as the total amount of study drug taken in one cycle.

The standard dose intensity is defined as the cumulative planned dose for cycle 1.

The relative dose intensity (RDI) is calculated by dividing the average delivered dose intensity over the standard dose intensity, expressed as a percentage.

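### Survival follow-up stops 12 months after each patient's own end of treatment, so Kaplan-Meier OS beyond month 12 is censored by treatment failure and is likely to read modestly high

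*Combined protocol and SAP*

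**What the plan says.** Section 7.10: "Subjects will be followed for 12 months after end of treatment (EoT) visit or until death, whichever occurs first". Section 6.1.3.2 and the last column of Table 2 give the same length, counted from the last dose: "every 3 months ± 14 days after last dose for 12 months". Section 7.10.2 schedules the assessments "for 12 months after the EoT visit, if feasible and clinically appropriate", for patients who have not progressed, with a telephone call as the minimum.

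Section 12.4.3: "Overall Survival (OS) will be calculated from the date of start of study therapy to the date of death due to any cause". It adds that OS is analysed in the same way as PFS. That means Kaplan-Meier, and it also carries over the PFS censoring date, the last assessment without evidence of disease. No OS-specific censoring rule is given.

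Under section 7.9, "treatment may continue until one of the following criteria applies": progression, intercurrent illness, unacceptable toxicity, withdrawal, or a change in the patient's condition. On duration, the Protocol Summary says: "Participants are estimated to receive study treatment for approximately 10 months".

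Two places disagree with the 12 months. Table 2 footnote 5b has calls "every 3 months for 18 months to inquire about" survival and disease status, for patients whose disease is not progressing. Sections 7.9 and 8.2 say: "All patients will be followed until disease progression, withdrawal of consent, death or loss to follow up".

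**The concern.** The OS clock starts at first dose, but the follow-up clock starts when treatment stops. A patient who stops at month 2 can be observed to month 14, one who stops at month 10 to month 22, and one who stops at month 20 to month 32. What stops treatment is mostly progression, toxicity or decline, and these also predict death. Kaplan-Meier assumes that patients censored at a given time have the same outlook as those still followed. Here the 12-month rule itself breaks that assumption, and perfect contact does not repair it.

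OS is a stated objective, with quartiles and confidence intervals planned. A confidence interval shows sampling error; it does not show a shift caused by the censoring rule. The study stays open until the last enrolled patient has finished a year of follow-up, so deaths among early failures could go unrecorded while the trial is still running.

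**Working it through.** **What the plan gives.** There is no OS assumption, event count or precision target to reproduce. The planned participant time, 10 + 1 + 12 = 23 months, agrees with the stated approximate 24.

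**Inputs.** Treatment duration: exponential, median 10 months (the Protocol Summary says only about 10 months; the distribution is assumed). Share of treatment ends that are deaths: 10% (assumed). Post-treatment survival: exponential, median m = 7, 9 or 12 months (assumed). Every contact is made.

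**Formulas.** Let a = ln 2/10 = 0.0693 and b = ln 2/m per month.

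- Ratio of survivors off treatment to survivors on treatment: r(t) = [0.9a/(b − a)] × [1 − exp(−(b − a)t)].
- True OS: S(t) = exp(−at) × [1 + r(t)].
- Death rate among survivors: h = (0.1a + b·r)/(1 + r).

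Under the 12-month rule, the off-treatment patients still observed after month 12 are those who stopped within the last 12 months. The observed ratio therefore stays at r(12) while the true ratio keeps growing. The Kaplan-Meier curve tends to KM(t) = S(12) × exp[−h₁₂(t − 12)], where h₁₂ is h evaluated at r(12).

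**Worked case, m = 7.** b = 0.0990 and b − a = 0.0297.

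- r(12) = 2.10 × (1 − 0.700) = 0.630; r(24) = 1.071.
- h₁₂ = (0.00693 + 0.0990 × 0.630)/1.630 = 0.0425. The true rate at month 24 is 0.0546.
- S(12) = 0.435 × 1.630 = 0.709. No one is censored by the rule before this point.
- True S(24) = 0.1895 × 2.071 = 0.392. KM(24) = 0.709 × exp(−0.510) = 0.426, which is 3.4 points high.
- KM median = 12 + ln(0.709/0.5)/0.0425 = 20.2 months. Solving S(t) = 0.5 gives a true median of 19.4.

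| m (months) | True 24-month OS | KM reads | True median | KM reads |
|---|---|---|---|---|
| 7 | 39.2% | 42.6% | 19.4 | 20.2 |
| 9 | 44.8% | 48.4% | 21.7 | 23.1 |
| 12 | 51.6% | 55.0% | 24.8 | 27.2 |

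Simulation agrees, and censoring at a common calendar date returns the true medians.

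**Treatment duration.** If 10 months is a mean (a = 0.1), the median shifts by only 0.2 to 1.0 months. If treatment lasts longer, the median shifts more. The Summary's Study Duration entry speaks of a 24-month median treatment duration; with a = ln 2/24 and m = 7, a true median of 34.0 months reads 39.4.

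**A second model.** True median OS was set at 19.2 months and median PFS at 7.7 to 12.2 months, both from the Background, with a constant post-progression hazard. The bias is 0 at month 12, +1.0 to +1.4 points at 18, +2.6 to +3.6 at 24, and +4.3 to +6.6 at 36. The KM median reads 19.8 to 20.0. When end of treatment is made independent of death, the bias is about 0.

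**Sensitivity.** Varying the shape of the post-progression hazard and adding shared frailty gives −0.9 to +7.1 points at 24 months. The one clear reversal needs a steeply falling hazard (Weibull shape 0.5), no shared prognosis and median PFS of 7.7 months.

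**The conflicting rules.** An 18-month window (footnote 5b) still leaves +0.6 points at month 24 and +2.4 at month 36. Ending survival follow-up at progression (literal 7.9 and 8.2) would give a 24-month OS of about 80% against a true 39%.

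**The case against.** The effect is small against the noise. With 26 patients the sampling SD of 24-month OS is about 10 to 11 points, roughly three times the shift. OS is exploratory and descriptive, and the two-stage rule uses response only. All of this stands, and it limits the weight of the point.

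The direction is not guaranteed either. It requires patients more than 12 months past treatment to die at a higher rate than those still observed. That is plausible and held in nearly all scenarios, but it is an assumption.

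A reader might infer three stronger things that the documents do not support:

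- *That the whole OS curve is biased.* The rule censors no one before month 12.
- *That the median could be several months too high because early progressors also die sooner afterwards.* The size depends on how shared prognosis is modelled, and the documents give nothing to fix it. A log-normal frailty (SD 0.6) on both hazards gave 1.5 to 3.0 months (20.8 read as 22.3; 23.8 read as 26.8).
- *That a comparison with the 19.2-month median OS of the clarithromycin-pomalidomide-dexamethasone study would flatter ClaSPd.* No such comparison is planned. That study had a median of 5 prior therapies, against two to four lines here, and its follow-up rule is not given.

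**Conclusion.** The point holds as a modest limitation of an exploratory endpoint. Follow-up time for OS depends on treatment failure by design, no section sets a common survival cut-off, and complete contact does not cure it. OS to month 12 is sound. After that the estimate probably reads high: about 3 to 4 points at 24 months and 0.8 to 2.4 months on the median. These sizes rest on exponential times, a 10-month median treatment duration, 10% of treatment ends being deaths, and post-treatment medians of 7 to 12 months. The response-rate conclusion is unaffected.

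The correction is still worth making. It costs little, and these sections need an edit anyway: the documents give three different ends of follow-up, and the one tied to progression, or the PFS censoring date applied to OS, would do far more damage than the 12-month rule.

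**What to change.** - **Sections 7.10, 7.10.2, 6.1.3.2 and Table 2:** keep 12 months for the disease assessments. Add survival status, by telephone or medical record, for every treated patient, including after progression, to one common date. The end-of-study date already defined in 7.10 is the natural choice; section 3.4 words the end of study differently, so name one date. A fixed month-37 cut-off (13 + 24) would be worse: under the assumptions above, about 29% of patients have a planned 12-month window running past it, and that follow-up would be lost.
- **Section 12.4.3:** state that OS is censored at that date or, if earlier, the date last known alive, and not at the PFS date of last assessment without evidence of disease.
- **Table 2 footnote 5b, sections 7.9 and 8.2:** bring the 18 months, the restriction to non-progressing patients, and the end of follow-up at progression into line with this rule.

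Cost: an amendment, consent wording for continued survival status, and a few extra calls or chart checks per patient. No visits or procedures are added.
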